3. STUDY DESIGN

This is a Phase 2, multicenter, randomized, parallel-group, placebo-controlled, double-blind, dose-ranging study to evaluate the efficacy and safety of INCB054707 (15, 45, and 75 mg QD) over a 24-week double-blind PC period followed by a 28-week double-blind extension period (INCB054707 45 mg and 75 mg QD). The study will enroll approximately 160 men and women aged 18 to 75 years with nonsegmental vitiligo, with depigmented areas including T-BSA \geq 8%, T-VASI \geq 8, F-BSA \geq 0.5%, and F-VASI \geq 0.5.

Participants will be screened for up to 32 days before the first dose of study drug. Participants who meet all study entry criteria and none of the exclusion criteria will return to the study site on Day 1 of dosing and be randomized to 1 of 4 treatment groups. Participants will be stratified based on T-BSA involvement (8.0%-20.0% and > 20.0%).

Participants will receive double-blinded study treatment of placebo or 1 of 3 doses of INCB054707 (15, 45, or 75 mg) QD for 24 weeks. Participants who complete the Week 24 will enter the 28-week double-blind extension period with 45 mg QD (for participants who received 45 mg during the PC period) or 75 mg QD (for participants who received placebo, 15 mg, or 75 mg during the PC period), with a safety follow-up visit scheduled 4 weeks after the last dose of study drug.

The study schema is shown in Figure 1.

The primary analysis will occur after the primary database lock, when all participants have completed or discontinued from the PC, double-blind treatment period.

The final analysis will occur when all participants have completed or withdrawn from the study.

3.1. Randomization

Approximately 160 participants will be randomized 1:1:1:1 to 1 of 3 INCB054707 treatment groups or the placebo group (approximately 40 participants per group).

Participant randomization will be stratified based on T-BSA involvement (8.0%-20.0%) and > 20.0%).

3.4. Schedule of Assessments

Refer to Protocol Amendment 2 dated 09 FEB 2022 for a full description of all study procedures and assessment schedules for this study.

4. DATA HANDLING DEFINITIONS AND CONVENTIONS

4.1. Scheduled Study Evaluations and Study Periods

4.1.1. Day 1

Day 1 is defined in Table 2 for each period. Note that the treatment groups for each period are described in Section 5.2.

Treatment Period	Treatment Group	Day 1
PC period	Placebo INCB054707 15 mg INCB054707 45 mg INCB054707 75 mg	The day the first dose of study drug (INCB054707 or placebo) is administered to the participants in the PC period.
Extension period	Placebo to INCB054707 75 mg INCB054707 15 mg to 75 mg INCB054707 45 mg INCB054707 75 mg	The day the first dose of study drug (INCB054707 45 mg or 75 mg) is administered to the participants in the extension period.
Throughout study participation	INCB054707 45 mg INCB054707 75 mg	The day the first dose of study drug (INCB054707 45 mg or 75 mg) is administered to the participants in the PC period.

Table 2:Definition of Day 1

For randomized participants not treated with any study drug, Day 1 is defined as the day of randomization.

4.1.2. Study Day

If a visit/reporting date is on or after Day 1, then the study day at the visit/reporting date will be calculated as

```
Day \# = (visit/reporting date - Day 1 date + 1).
```

If the visit/reporting date is before Day 1, then the study day at the visit/reporting date will be calculated as

Day # = (visit/reporting date - Day 1 date).

A study day of -1 indicates 1 day before Day 1.

4.1.3. Baseline Value

Baseline is the last nonmissing measurement obtained before the first administration of INCB054707 or placebo in the PC period, unless otherwise defined.

For randomized participants not treated with any study drug, baseline is defined as the last nonmissing assessment before or on the day of randomization for all parameters.

For participants who continue in the extension period, baseline is defined as follows:

- For efficacy evaluation in the extension period, baseline is the last nonmissing measurement obtained before the first administration of study drug in the PC period, unless otherwise defined.
- For safety evaluation in the extension period, baseline is the last nonmissing measurement obtained before the first administration of study drug in the extension period, unless otherwise defined.

When scheduled assessments and unscheduled assessments occur on the same day and the time of the assessment or time of first dose is not available, use the following convention to determine baseline:

- If both a scheduled and an unscheduled visit are available on the day of the first dose and the time is missing, use the scheduled assessment as baseline.
- If all scheduled assessments are missing on the day of the first dose and an unscheduled assessment is available, use the unscheduled assessment as baseline.

4.1.4. Handling of Missing and Incomplete Dates

In general, values for missing dates will not be handled unless methods for handling missing dates are specified in this section or relevant sections. The original reported dates collected in the eCRF should be used in all relevant listings. The following rules will be used for handling partial dates for analyses requiring dates.

When calculating the time since diagnosis of nonsegmental vitiligo, a partial diagnosis date will be handled as follows in the calculation:

- If only the day is missing, then the first day of the month will be used.
- If both the month and day are missing, then 01 JAN of the year will be used.
- If the diagnosis date is completely missing, then the time since diagnosis will not be calculated.

When the date of the last dose is used in deriving variables such as duration of treatment or TEAE flag, a missing or partial date of the last dose will be handled as follows:

- If only the day is missing, then the earlier date of the last day of the month or the date that the participant discontinued treatment will be used.
- If both the month and day are missing, then the earlier date of 31 DEC of the year or the date that the participant discontinued treatment will be used.
- Otherwise, the date that the participant discontinued treatment will be used as the date of the last dose.

4.2. Variable Definitions

The following variables will only be calculated if not reported in the eCRF.

4.2.1. Body Mass Index

Body mass index will be calculated as follows:

Body mass index $(kg/m^2) = [weight (kg)] / [height (m)]^2$.

4.2.2. Prior and Concomitant Medication

Prior medication is defined as any nonstudy medication started before the first dose of INCB054707 or placebo in the PC period.

In the PC period, concomitant medication is defined as any nonstudy medication that is started accordingly:

- Before the date of first administration of INCB054707 or placebo in the PC period and is ongoing throughout the study or ends on/after the date of first study drug administration during the PC period.
- On/after the date of first administration of INCB054707 or placebo in the PC period and is ongoing or ends during the PC period.

In the extension period, concomitant medication is defined as any nonstudy medication that is started accordingly:

- Before the date of first administration of INCB054707 in the extension period and is ongoing throughout the study or ends on/after the date of first study drug administration during the extension period.
- On/after the date of first administration of INCB054707 in the extension period and is ongoing or ends during the extension period.

A prior medication could also be classified as "both prior and concomitant medication" if the end date is on or after first dose of INCB054707 or placebo. In the listing, it will be indicated whether a medication is only prior, only concomitant, or both prior and concomitant.

For the purposes of analysis, all medications will be considered concomitant medications unless the medications can unequivocally be defined as not concomitant.

5. STATISTICAL METHODOLOGY

5.1. General Methodology

Unless otherwise noted, SAS[®] software (SAS Institute Inc, Cary, NC; v9.1 or later) will be used for the generation of all tables, graphs, and statistical analyses. Descriptive summaries for continuous variables will include but not be limited to the number of observations, mean, standard deviation, median, minimum, and maximum. Descriptive summaries for categorical variables will include the number and percentage of participants in each category.

5.2. Treatment Groups

This is a randomized, double-blind, placebo-controlled, dose-ranging study followed by a double-blind extension period. Table summaries, unless otherwise indicated, will present data by treatment group. The results will be summarized and presented separately for the PC period and the extension period, unless otherwise specified.

For the PC period, the treatment groups will be placebo and INCB054707 15, 45, and 75 mg.

For the extension period, the participants will be grouped as follows according to the treatment they received during the PC period:

- Placebo to INCB054707 75 mg
- INCB054707 15 mg to 75 mg
- INCB054707 45 mg
- INCB054707 75 mg

5.3. Analysis Populations

5.3.1. All-Randomized Population

The all-randomized population will include all participants who were randomized.

5.3.2. Intent-to-Treat Population

All participants who were randomized to the study constitute the ITT population. Treatment groups for this population will be defined according to the treatment assignment at the time of randomization regardless of the actual study treatment the participant might apply during their participation in the PC period.

The ITT population will be used for the summary of demographics, baseline characteristics, participant disposition, and analyses of all efficacy data in the PC period.

5.3.3. Safety Population

The safety population will include all participants who received at least 1 dose of INCB054707 or placebo during the PC period. Treatment groups for this population will be determined according to the actual treatment the participant receives on Day 1 in the PC period regardless of assigned study treatment.

All safety analyses for the PC period will be conducted using the safety population.

5.3.4. Extension Evaluable Population

All analyses for the extension period will be conducted with the extension evaluable population, which includes all participants who received at least 1 dose of INCB054707 during the extension period.

6. **BASELINE, EXPOSURE, AND DISPOSITION**

Appendix A provides a list of data displays. Sample data displays are included in a separate document.

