2.2.1. Scientific Rationale for Study Design

INCB054707 is an oral small-molecule JAK1 inhibitor and has been evaluated in 36 participants with HS in 2 clinical studies with oral doses of up to 90 mg for 8 weeks. During the treatment period, INCB054707-treated participants demonstrated improvement, characterized as decreased number of abscesses and inflammatory nodules, decreased HS-associated pain, and improved quality of life. Observed AEs were mild to moderate in intensity and mostly unrelated to study medication, with no associated SAEs or withdrawals. Immunological commonalities exist between HS and vitiligo, in which lesions have increased expression of lymphocyte-recruiting chemokines, including CXCL10 (Vosseen et al 2019), and elevated IFN- γ levels (Banerjee et al 2017). Treatment of patients with vitiligo for 24 weeks with the topical JAK1/2 inhibitor ruxolitinib cream demonstrated that inhibition of the JAK-STAT pathway leads to repigmentation (Rosmarin et al 2020). [REDACTED]

[REDACTED]

[REDACTED]

[REDACTED]

In the proposed study, the clinical safety and efficacy of 3 doses of INCB054707 (15, 45, and 75 mg) compared with placebo will be evaluated in male and female adult participants with extensive vitiligo (T-BSA \geq 8%, T-VASI \geq 8, F-BSA \geq 0.5%, and T-VASI \geq 0.5) for 24 weeks, which is consistent with the duration of other systemic therapies and with narrow-band UVB phototherapy (Hamzavi et al 2004). Efficacy will be assessed via changes in the [REDACTED] affected by vitiligo lesions, [REDACTED] and T-VASI, [REDACTED] and photography. [REDACTED]

[REDACTED]

[REDACTED]

[REDACTED]

[REDACTED]

With the goal of obtaining long-term efficacy and safety data for the compound (up to 52 weeks in total), after the 24-week placebo-controlled period, all participants will enter into a double-blind extension period for 28 weeks and will receive either 45 mg or 75 mg QD, followed by a 4-week safety follow-up period [REDACTED]

[REDACTED] to monitor safety and potential change in pigmentation after discontinuation or completion of treatment with INCB054707.

It is expected that the outcome of this study will be instrumental in informing dose selection to be evaluated in a potential Phase 3 study in the future.

[REDACTED]

[REDACTED]

[REDACTED]

[REDACTED]

[REDACTED]

[REDACTED]

[REDACTED]

[REDACTED]

[REDACTED]

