6.2. Disposition of Participant

The number of participants enrolled by country and/or site will be summarized for the ITT population by treatment group and overall.

The following will be summarized by treatment group and overall for the ITT population in the PC period:

- Number (%) of participants who were randomized
- Number (%) of participants who were treated in the PC period
- Number (%) of participants who completed treatment in the PC period through Week 24
- Number (%) of participants who discontinued study treatment in the PC period with a primary reason for discontinuation
- Number (%) of participants who withdrew from the study in the PC period with a primary reason for withdrawal

The following will be summarized by treatment group and overall for the extension evaluable population in the extension period:

- Number (%) of participants who were treated in the extension period
- Number (%) of participants who completed treatment in the extension period
- Number (%) of participants who discontinued study treatment in the extension period with a primary reason for discontinuation
- Number (%) of participants who completed the study
- Number (%) of participants who withdrew from the study in the extension period with a primary reason for withdrawal

6.3. **Protocol Deviations**

Protocol deviations recorded will be summarized by treatment group and overall, for the ITT population in the PC period and the extension evaluable population in the extension period, and listed.

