7.1. General Considerations

All by-visit analyses for the extension evaluable population will include the follow-up period if the data are available, unless otherwise specified.

Unless otherwise stated, the strata identified in the randomization process will be used in all efficacy analyses.

Total body VASI (T-VASI) is calculated using a formula that includes contributions from all body regions (possible range: 0-100) as follows:

VASI = $\sum_{\text{all body sites}} [\text{Hand Units}] \times [\text{Residual Depigmentation}]$

The body is divided into the following 6 separate and mutually exclusive sites: (1) head/neck, (2) hands, (3) upper extremities (excluding hands), (4) trunk, (5) lower extremities (excluding feet), and (6) feet. The percentage of vitiligo involvement is estimated in hand units (%BSA) by the same investigator during the entire course of the study. Hand unit is based on the participant's hand size. The investigator uses their hand to mimic the participant's hand size to evaluate %BSA vitiligo involvement. The degree of depigmentation for each body site is determined and estimated to the nearest of the following percentages: 0%, 10%, 25%, 50%, 75%, 90%, or 100%. The T-VASI is then derived by multiplying the values assessed for the vitiligo involvement by the percentage of affected skin for each body site and summing the values of all body sites together (Hamzavi et al 2004).

The T-VASI50 is defined as at least 50% reduction from baseline in T-VASI.

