8.2.2. Adverse Event Summaries

Adverse events will be summarized by treatment group and overall INCB054707 dose groups for the safety population in the PC period. For the extension evaluable population in the extension

period and for participants who took INCB054707 45 mg or 75 mg throughout study participation, AEs will be summarized by treatment group and overall.

An overall summary of AEs will include the following:

- Number (%) of participants reporting any TEAEs
- Number (%) of participants reporting any serious TEAEs
- Number (%) of participants reporting any Grade 3 or higher TEAEs
- Number (%) of participants reporting any treatment-related TEAEs
- Number (%) of participants who temporarily interrupted study treatment because of TEAEs
- Number (%) of participants who permanently discontinued study treatment because of TEAEs
- Number (%) of participants who had a fatal TEAE

The following summaries will be produced by MedDRA term (if 10 or fewer participants appear in a table, a listing may be appropriate):

- Summary of TEAEs by MedDRA SOC and PT
- Summary of TEAEs by MedDRA PT in decreasing order of frequency
- Summary of TEAEs by MedDRA SOC, PT, and maximum severity
- Summary of TEAEs by MedDRA SOC, PT, and CTCAE grade category
- Summary of Grade 3 or higher TEAEs by MedDRA SOC and PT
- Summary of Grade 3 or higher TEAEs by MedDRA PT in decreasing order of frequency
- Summary of serious TEAEs by MedDRA SOC and PT
- Summary of serious TEAEs by MedDRA PT in decreasing order of frequency
- Summary of treatment-related TEAEs by MedDRA SOC and PT
- Summary of treatment-related TEAEs by MedDRA PT in decreasing order of frequency
- Summary of Grade 3 or higher treatment-related TEAEs by MedDRA SOC and PT
- Summary of treatment-related serious TEAEs by MedDRA SOC and PT
- Summary of TEAEs with a fatal outcome by MedDRA SOC and PT
- Summary of TEAEs leading to dose interruption by MedDRA SOC and PT
- Summary of TEAEs leading to discontinuation of study drug by MedDRA SOC and PT
- Summary of TEAEs requiring concomitant medications by MedDRA SOC and PT

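### Does limiting extension analyses to participants dosed in the extension distort the 52-week T-VASI results for the 45 mg and 75 mg arms?

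*SAP*

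**What the plan says.** SAP 5.3.4 sets the population for the extension: "All analyses for the extension period will be conducted with the extension evaluable population, which includes all participants who received at least 1 dose" (a dose taken in the extension itself). SAP 5.3.2 gives the ITT population, among other uses, to "analyses of all efficacy data in the PC period". Entry depends on finishing the placebo-controlled (PC) period: "Participants who complete the Week 24 will enter the 28-week double-blind extension period with 45 mg QD" if they were on that dose, and with 75 mg if they came from placebo, 15 mg or 75 mg (SAP 3; Protocol 4.1).

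The efficacy baseline does not restart. SAP 4.1.3 says: "For efficacy evaluation in the extension period, baseline is the last nonmissing measurement obtained before the first administration of study drug", meaning the first PC dose. SAP 7.1 adds: "All by-visit analyses for the extension evaluable population will include the follow-up period if the data are available". T-VASI is scheduled at Week 52 (Protocol Table 4).

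Three other parts of the SAP bear on the point:
- **Disposition (6.2)** counts, by arm, participants randomised, completing Week 24, and stopping or withdrawing with reasons. For the extension it begins with "Number (%) of participants who were treated in the extension period".
- **Demographics (6.1.1)** are shown for both the ITT and the extension evaluable populations.
- **Periods (4.1.1, Table 2)** are three: PC, extension, and a third spanning all of study participation. The third applies only to 45 mg and 75 mg and starts at the first PC dose. It is used for exposure (6.4) and adverse events (8.2.2: "for participants who took INCB054707 45 mg or 75 mg throughout study participation, AEs will be summarized by treatment group and overall").

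**The concern.** For the placebo and 15 mg arms, which switch dose, an entrants-only population is the natural choice. The 45 mg and 75 mg arms are different. With the pre-treatment baseline, their Week 52 change covers 52 weeks on the randomised dose, yet the denominator is fixed by an event at Week 24, after randomisation. If people who do badly leave before Week 24, the Week 52 response rate among those remaining is too high. If people who do well leave, it is too low. If leaving also differs between the two doses, a side-by-side reading of 45 mg and 75 mg could be distorted.

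This would matter because Protocol 2.2.1 gives long-term efficacy and safety data, up to 52 weeks, as the purpose of the extension, and expects the study to inform dose selection for a possible Phase 3 study.

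**Working it through.** **1. Arm size.** SAP 3.1: about 160 randomised 1:1:1:1, so 160/4 = 40 per arm. This agrees with the SAP's figure.

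**2. What is affected.** The primary hypothesis is 75 mg against placebo at Week 24 (SAP 7.3). The key secondary endpoint is T-VASI50 at Week 24 (SAP 7.5). Both belong to the PC period and so to ITT. After Week 24 no placebo arm remains. The readable text has no Week 52 endpoint and no test of 45 mg against 75 mg.

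**3. Whether 5.3.4 governs the summary in question.** It covers analyses for the extension period. A 52-week summary of the two constant-dose arms fits the third period of Table 2 at least as well, and that period starts at the first PC dose. No readable efficacy text uses it. However, the endpoint rows after safety in SAP Table 1, the text of 7.4.1, the methods of 7.5 and the display list in Appendix A are not shown. Nonresponder imputation is in the SAP abbreviation list with no readable use, so some missing-data rule lies in the hidden text. It cannot be said that an all-randomised summary is absent.

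**4. Size, on assumptions.** The documents show neither dropout nor Week 52 response. Assume p = 40% T-VASI50 at Week 52 among all 40 randomised. Let s be the share entering and r the response among non-entrants.

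- Error of the entrant-only rate: (p - (1 - s)r)/s - p = ((1 - s)/s)(p - r).
- Error if non-entrants are counted as nonresponders, before any later stopping: (p - (1 - s)r) - p = -(1 - s)r.

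For s = 36/40 = 0.90 and r = 20%: entrant-only (0.10/0.90)(0.40 - 0.20) = +2.2 points; nonresponder counting -0.10 × 0.20 = -2.0 points.

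Errors in percentage points, entrant-only / nonresponder counting:

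| Entering of 40 | r = 0% | r = 20% | r = 40% | r = 60% |
|---|---|---|---|---|
| 38 | +2.1 / 0 | +1.1 / -1.0 | 0 / -2.0 | -1.1 / -3.0 |
| 36 | +4.4 / 0 | +2.2 / -2.0 | 0 / -4.0 | -2.2 / -6.0 |
| 34 | +7.1 / 0 | +3.5 / -3.0 | 0 / -6.0 | -3.5 / -9.0 |
| 32 | +10.0 / 0 | +5.0 / -4.0 | 0 / -8.0 | -5.0 / -12.0 |

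The two errors are equal in size when (p - r)/s = r, that is r = p/(1 + s). With p = 0.40 this is 0.40/1.95 = 20.5% at 38 entering and 0.40/1.80 = 22.2% at 32 entering. Nonresponder counting is closer only below that value, roughly half the arm's own response rate.

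**5. Between the two doses.** Suppose both arms are truly at 40%, with 36 (45 mg) and 32 (75 mg) entering. For r = 0%, 20%, 40%, 60%, the spurious difference (75 mg minus 45 mg) is:
- Entrant-only: 50.0 - 44.4 = +5.6; 45.0 - 42.2 = +2.8; 0; 35.0 - 37.8 = -2.8.
- Nonresponder counting: 40 - 40 = 0; 36 - 38 = -2.0; 32 - 36 = -4.0; 28 - 34 = -6.0.

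Swapping the entry numbers reverses every sign. The standard error of a 40% against 40% difference with 40 per arm is sqrt(2 × 0.40 × 0.60/40) = 11.0 points, so the largest entrant-only distortion shown is about half of it (5.6/11.0 = 0.51).

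**The case for a change.** The strongest case for acting is that selective loss is plausible from the protocol itself. Protocol 4.2 ties continued treatment to benefit. Protocol 2.3.1 reports platelet falls at 60 mg and above with a dose-related trend, and 75 mg lies in that range while 45 mg does not. The SAP follows these two arms from the first dose for exposure and adverse events, so doing the same for efficacy would be consistent and would need one table.

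Part of this stands. Read literally, 5.3.4 does condition on entry, and a Week 52 rate in that population describes entrants, not everyone randomised. The published checks on selection are also limited: the extension population gets demographics (6.1.1), but baseline disease characteristics are planned for ITT only (6.1.2).

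The rest does not make it an error. The platelet data show plausibility at most: counts in healthy participants stayed within the normal range, and the affected hidradenitis suppurativa participants resumed dosing and completed. Nor does dividing by 40 reveal a bias. For example, 18 responders among 36 entrants is 50.0%, and 18/40 is 45.0%. That 5.0-point gap follows by definition from setting every non-entrant to nonresponse. It answers a different question, and any reader with extension responder counts and the disposition table can make the same division.

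**Conclusion.** The concern does not hold. The extension evaluable population is a conventional, clearly labelled choice for describing an extension, with entry numbers reported by arm. No Week 24 conclusion depends on it, and no readable Week 52 endpoint or dose comparison does either.

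On the assumed inputs (40 per arm, 40% response, 32 to 38 entering), the entrant-only rate for one arm is off by between +10.0 and -5.0 points, and is exact if non-entrants respond like the rest of their arm. The between-dose distortion in the scenario of 36 against 32 entering stays within 5.6 points either way. Counting non-entrants as nonresponders on the same inputs is off by between 0 and -12.0 points, and is better only when non-entrants respond at less than about 20.5% to 22.2%. Neither denominator is right in general.

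Wanting the second one as well is a preference for an extra table, and the redacted text may already provide it. All of these sizes rest on assumed entry and response rates, because the documents show neither.
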